Similarly, surgical decompression of trigger sites has previously been shown to have superior clinical outcomes to medical management, through a randomized, blinded controlled-trial performed at Case Western Reserve in 2009.⁷ Patients either received actual decompression of the trigger sites, or sham surgery (exposure and visualization of the trigger sites, without decompression). At one-year follow-up, the group who underwent actual surgery demonstrated a statistically higher proportion with significant improvement in their migraines (83.7% vs. 57.7%, p=0.014), and with complete elimination of their migraines (57.1% vs. 3.8%, p<0.001). Several other reports have confirmed the good clinical outcomes of surgery demonstrated in this trial,^{6,8} and surgical decompression is now commonly performed by several surgeons around the United States.

Prognostic factors predicting the success of surgical decompression in migraine headache treatment include older age of migraine onset, visual symptoms/aura, and 4-site decompression. Factors predicting failure of surgery include excessive operative blood loss, and surgery on only one or two trigger sites.⁹

One criticism of the studies on migraine surgery has been that most of the results have originated from the same institution (Case Western Reserve), and from the same author (Guyuron). While several studies at other institutions have demonstrated positive outcomes of migraine surgery,⁶ these have only included a small number of patients.

In addition, the sham surgery randomized-controlled trial has been criticized for not clarifying any prior treatments that patients had undergone before migraine surgery, and for not showing how medication use patterns changed after surgery. Another criticism of that study was the fact that patients were examined by neurologists before the study but not after the study, and that surgery was performed on some patients with episodic migraines, who are known to not benefit from botulinum toxin. It is unclear what migraine types are most likely to benefit from surgical decompression.

Our goal is to perform a multi-center, prospective trial to demonstrate the effectiveness of migraine surgery, which would address the criticisms mentioned above. The main aim is to demonstrate that the positive results demonstrated by Guyuron *et al* are reproducible at other institutions and by other surgeons using similar techniques on different patient populations.

II. Objectives

Our goals in this study are:

- 1. To evaluate the effectiveness of surgical decompression in migraine headaches prospectively, using validated instruments, and to compare it to the effectiveness of a botulinum toxin injection protocol
 - a. Our hypothesis is that migraine surgery decreases the frequency and severity of migraine headaches significantly, as measured by

validated questionnaires, and that the reduction is greater and more sustainable than that seen with a botulinum toxin injection protocol

- 2. To determine which types of migraine headaches benefit most from surgical decompression and/or botulinum toxin injection
- 3. To identify prognostic factors for the success or failure of surgical decompression in migraine headache
 - a. These have been demonstrated in a previous study,⁹ but have not evaluated in a multi-center fashion.
- 4. To compare the long-term direct and indirect costs in patients with migraine headaches undergoing botulinum toxin A injections versus surgical decompression
 - a. We hypothesize that, over the long-term, surgical decompression is more cost-efficient than a botulinum toxin injection protocol

III. Procedures

a. Research design

This is a **prospective, multi-center** evaluation of the short, medium and long-term efficacy of surgical decompression in migraine headaches, comparing it to the efficacy of a botulinum toxin injection protocol.

b. Sample

Inclusion criteria:

-Patients with migraines related to a trigger site at the location of a branch of a cranial nerve (frontal, temporal, occipital)

-Patients with chronic migraine (≥15 days per month) as dictated by the FDA indication for botulinum, and as diagnosed by a board-certified neurologist

Exclusion criteria:

-Patients deemed by the senior author or the neurologist to not have migraine headaches, but an alternative diagnosis

-Patients with systemic conditions that make them poor candidates for surgery (coronary artery disease, uncontrolled diabetes mellitus, etc...)

-Patients with migraines related to inferior turbinate hypertrophy or septal deviation -Patients with a frontal, temporal or occipital trigger point who do not respond to a diagnostic botulinum toxin injection

-Hypersensitivity to any botulinum toxin preparation or to any of the components in the formulation

-Infection at the proposed injection site for botulinum

Sample size (power analysis)

Since there are several endpoints in this study, the required sample size can be calculated in several ways:

-Using efficacy as an endpoint:

In Janis *et al*,⁶ patients undergoing botulinum toxin injections had an average improvement in their Migraine Headache Index of 87.5%. In comparison, patients undergoing surgery had an average improvement of 96.6%.

Assuming a standard deviation of 20%, an alpha error of 5%, and a power of 80%, the required sample size using this method is **30 patients in each group**.

-Using total cost of treatment as an endpoint:

Assuming an average injection volume of 75 Units of botulinum toxin every 3 months, and assuming a cost of \$12-15 per Unit, the estimated cost of a botulinum toxin A injection protocol over one year is \$3,600-\$4,500.

In comparison, the estimated cost of surgery (including facility fee, surgeon fee, preoperative testing and follow-up) is \$8,378.¹⁰

Therefore, in order to demonstrate a financial superiority of surgery versus botulinum toxin, the patients would need to be follow-up for 1.9 to 2.3 years. Assuming a study follow-up of 2.5 years, and average costs of botulinum and surgery of $$10,125 \pm $2,000$ and $$8,378 \pm $2,000$, respectively, and assuming an alpha error of 5%, a power of 80%, the required sample size using this method is **16 patients in each group**.

-Using treatment success by trigger site as an endpoint:

According to Larson *et al*,⁹ the success rates for surgery by trigger site were as follows: Frontal 83.3%, temporal 75.8%, and occipital 45.5%. In order to discern a difference between the outcomes for the two sites with the closest outcomes (frontal and temporal), and assuming a standard deviation of 10%, an alpha error of 5%, and a power of 80%, the required sample size using this method is **14 patients in each group**.

Looking at the three methods above, keeping the method yielding the highest required number of participants, and accounting for any participant drop-out, we will seek to enroll **50 patients in each group.**

c. Detailed study procedures

A neurologist will evaluate patients presenting for evaluation for treatment of migraine headaches, for confirmation of the diagnosis of migraine. The type of migraine that they suffer from will be recorded. If the diagnosis of migraine is confirmed, they will sign an informed consent form, and they will be asked to complete a daily headache diary, and keep track of their 1) daily use of medications for migraines, 2) physician visits for migraines, 3) ER visits for migraines, 4) days of work lost due to migraines, 5) other costs directly related to migraines for 2 months. They will also be asked to

complete three questionnaires: the Migraine Work and Productivity Loss Questionnaire (MWPLQ),¹¹ the Migraine Disability Assessment questionnaire (MIDAS)¹² and the Migraine-Specific Quality of Life questionnaire (MSQ) at the time of enrollment.

All patients will undergo a history and physical examination, including an intranasal examination. This will include determination of the possible trigger site: frontal, temporal, occipital, and inferior turbinate/septum. The trigger site can be determined using a combination of three methods: 1) Physical examination, 2) Diagnostic botulinum toxin injection into a specific trigger point, and 3) Nerve block using a local anesthetic injected into a specific trigger point in patients having active symptoms.

The patients will be asked whether they prefer to undergo surgical decompression or a botulinum toxin protocol, and their preference will be recorded.

50 patients who prefer surgery, and who satisfy the inclusion and exclusion criteria, will be included in the study as **Group A**. The location of the trigger site(s) will be determined based on history, physical examination, a diagnostic botulinum toxin injection and/or a nerve block. If those patients are found to have a trigger site that responds to botulinum injection, they will undergo surgical decompression of their trigger site, as described in Janis *et al*⁶ and Guyuron *et al*.⁷ Those patients will be followed postoperatively. They will be asked to continue tracking their 1) daily use of medications for migraines, 2) physician visits for migraines, 3) ER visits for migraines, 4) days of work lost due to migraines, and 5) other costs directly related to migraines for 2 months. At 1 year, 2 years and 2.5 years postoperatively, they will be asked to fill the Migraine Work and Productivity Loss Questionnaire (MWPLQ), the Migraine Disability Assessment questionnaire (MIDAS) and the Migraine-Specific Quality of Life questionnaire (MSQ) again. They will also be examined by a board-certified neurologist at 1 year postoperatively.

A separate sample of 50 patients from the pool of patients undergoing the botulinum toxin injection protocol will be selected (Group B). Those patients will be matched to the individual patients in group A based on gender, age (in 5 year intervals), migraine severity (based on the Migraine Disability Assessment questionnaire, 5 –point intervals) and trigger site (pair-matching). For example, for a patient in Group A who is a 47 year-old woman with temporal migraines and a MIDAS severity score of 14, a patient on the botulinum injection protocol will be included in Group B is she is a 45 to 50 year old female with temporal migraines and a MIDAS severity score of 10 to 15.

The patients in group B will receive the botulinum injection protocol, and will continue to track their 1) daily use of medications for migraines, 2) physician visits for migraines, 3) ER visits for migraines, 4) days of work lost due to migraines, and 5) other costs directly related to migraines for 2 months. At 1 year, 2 years and 2.5 years after the start of the protocol, they will be asked to fill the Migraine Work and Productivity Loss Questionnaire (MWPLQ), the Migraine Disability Assessment questionnaire (MIDAS)

and the Migraine-Specific Quality of Life questionnaire (MSQ). They will also be examined by a board-certified neurologist at 1 year postoperatively.

The Botox injections and the surgeries are being done as part of the routine clinical care for the patients enrolled in the study. The only procedures being done solely for research purposes are having the patients fill out the surveys and diaries.

d. Measurements

The measurements will include

- 1) Number of migraine headaches per 30 days
- 2) Cost of migraine-related medications, physician visits, ER visits
- 3) Cost of days of work lost due to migraine as calculated from the Migraine Work and Productivity Loss Questionnaire (MWPLQ)
- Score on the Migraine Disability Assessment Questionnaire (MIDAS) (0-21)
- 5) Scores on the emotional, restrictive and preventive portions of the Migraine-Specific Quality of Life questionnaire (MSQ)

The following comparisons will be made for the above measurements:

-Within Group A, compare all measurements before surgery to 1 year, 2 years and 2.5 years after surgery, using a t-test

-Within Group B, compare all measurements before start of injection protocol to 1 year, 2 years and 2.5 years after injection protocol, using a t-test

-Compare all measurements between Group A and Group B using a paired t-test analysis

e. Internal validity

The study avoids confounding by virtue of the matched-pair analysis. The study avoids recall bias by having the patients fill-out the questionnaires preoperatively and postoperatively, rather than having them retrospectively assess their improvement after surgery.

Blinding is very difficult in such a study. In order to avoid experimenter bias, all assessment will be made by the patients themselves, without influence by the experimenters.

The main threat to internal validity is the possible placebo effect inherent to migraine headache treatments. This may threaten the validity of the data on differences in clinical outcomes between the two groups. It will not threaten the validity of the data on financial cost

f. External validity

Because this is a multi-center trial that includes different patient populations treated by different clinicians, this study is generalizable to the general population of patients with migraines in the United States.

g. Data analysis

Group B will be selected by matching individual participants to members of Group A based on gender, age, migraine severity and migraine location.

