Prospective, Multi-Center Evaluation of the Efficacy of Migraine Surgery

Statistical Analysis Plan

IRB Approval #:2015H0024

NCT02351544

Document Date Version: February 16, 2014

Principal Investigator: [name], FACS (The Ohio State University)

Outcomes

**Outcomes modeled were: MHI, MIDAS A, MIDAS B, MIDAS Total, MSQ Sum and MWPLQ7 Total

Data Analysis

Descriptive statistics, such as frequency and percents, were displayed for sex (male or female), treatment (Botox or Surgery) and site (OSU or MGH). Descriptive statistics, such as mean, standard deviation, median, lower quartile and upper quartile, were reported for age and the patient reported outcomes with the respect to their migraine for each time point (baseline, 1 year, 2 years and 2.5 years).

Each of six outcomes were highly skewed and therefore natural logarithm was applied to each one before it was modeled. A constant of 1 was added to outcome values before applying natural log function so as to include raw values of zeros.

Linear mixed models with a random effect for patient were used to evaluate the changes in each of six outcomes between two different treatments over time with inclusion of interaction between treatment and time. These models were used given to account for correlation between repeated measurements on the same patient and to account for missing data across time points. P-values for both the main and interaction effects of time and treatment were reported for each model and Tukey's post hoc method was used to adjust for pairwise comparisons. For the ease of interpretation, raw means and SDs are presented for each time point within specific treatment.

Analyses were performed using SAS v9.4 (SAS Institute; Cary, NC; www.sas.com). Statistical significance was defined as two-sided alpha<0.05.

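### The trial undertakes to show how medication use changes, but schedules no medication data at 1, 2 and 2.5 years and has no medication outcome in the SAP; prior treatments are not a named variable

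*Protocol*

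**What the plan says.** **The undertaking.** The Protocol's background (the text before section II) lists criticisms of the earlier sham-surgery trial. It was "criticized for not clarifying any prior treatments that patients had undergone before migraine surgery" and "for not showing how medication use patterns changed after surgery". The new trial is introduced as one "which would address the criticisms mentioned above".

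**Collection.** Under III.c, enrolled patients complete a headache diary and "keep track of their 1) daily use of medications for migraines", in a list of five items that ends "5) other costs directly related to migraines for 2 months". After surgery, Group A patients are treated similarly: "They will be asked to continue tracking their 1) daily use of medications for migraines", with the same five items and the same closing words. Group B has the same list. At 1, 2 and 2.5 years III.c schedules the MWPLQ, MIDAS and MSQ, and a neurologist examines patients at 1 year. No diary or medication log is mentioned at these times.

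**Measurement and analysis.** III.d includes the cost of migraine-related medications, physician visits and ER visits. III.d and III.g compare the measurements before treatment with those at 1, 2 and 2.5 years, and between groups. Objective 4 in section II is a comparison of long-term direct and indirect costs. The SAP states: "Outcomes modeled were: MHI, MIDAS A, MIDAS B, MIDAS Total, MSQ Sum and MWPLQ7 Total".

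**Prior treatments.** III.c requires a neurologist's evaluation and a history and physical examination. Matching uses gender, age, MIDAS score and trigger site. SAP descriptives cover sex, treatment, site, age and the patient-reported outcomes. The SAP model contains treatment, time, their interaction and a random patient effect.

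**The concern.** The other criticisms in the background are each met by a visible design feature: more than one centre, restriction to chronic migraine, and a neurologist's examination after treatment. The two on prior treatments and medication are not followed through in the same way.

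Medication matters for interpretation. A lower headache or disability score means one thing if patients take fewer drugs and another if they take more. If medication is not measured when the outcomes are, a reader at 1 to 2.5 years cannot tell which has happened. The direct-cost part of Objective 4 has the same gap, because physician and ER visits are tracked in the same log.

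Prior treatment matters because patients choose their group and Group B is drawn from patients on the injection protocol. If treatment history differs between groups, neither the matching nor the SAP model would account for it.

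**Working it through.** The plan gives no figure on this point to reproduce. The check sets the stated comparisons against the collection schedule.

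**Inputs**
- Follow-up: 2.5 years = 30 months (Protocol III.b, sample size; III.c).
- Comparison times: 12, 24 and 30 months (III.d, III.g).
- Medication log: 2 months at baseline and 2 months after treatment (III.c). The start of the second window is not stated.
- Instruments at the comparison times: MWPLQ, MIDAS, MSQ (III.c).

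**Step 1: coverage after treatment.** 2 / 30 = 0.067, or 6.7% of follow-up. With the baseline log, 2 + 2 = 4 months are tracked in all.

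**Step 2: distance to the comparison times.** Assume the second window starts at treatment. It then ends at month 2, which is 12 − 2 = 10, 24 − 2 = 22 and 30 − 2 = 28 months before the three comparisons.

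**Step 3: does the unstated start matter?** The comparison times are 24 − 12 = 12 and 30 − 24 = 6 months apart, both longer than 2 months. A single 2-month window can therefore include at most one of them, wherever it is placed. At least two of the three comparisons have no scheduled medication log.

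**Step 4: stated comparison against scheduled source**

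| Item | Compared at 1, 2, 2.5 years (III.d) | Source scheduled then (III.c) | SAP outcome |
|---|---|---|---|
| Medication cost | Yes | None named | No |
| Physician and ER visit cost | Yes | None named | No |
| Medication use (days, doses, class) | Not defined as a measurement | None named | No |
| MIDAS, MSQ, MWPLQ | Yes | The questionnaires | Yes |

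**Step 5: the other reading of the time limit.** The words "5) other costs directly related to migraines for 2 months" close a five-item list, so the limit could attach to the fifth item alone. Medication tracking would then have no stated end, and data might exist at all three visits. The SAP would still analyse none of it.

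**Step 6: prior treatments.** They do not appear in the eligibility criteria, the enrolment items, the matching factors, the SAP descriptives or the SAP model. The nearest provision is the general history.

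**The case against.** The best defence has five parts.

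1. *Medication is measured.* There is a log before and a log after treatment in both groups, so early within-patient change can be shown, and medication cost is a Protocol measurement. This stands. It would be tempting to infer that the trial collects no medication outcome and simply repeats the earlier trial's fault. The documents do not support that. They do support a narrower statement: medication is defined only as cost, which does not show days, doses or drug class, and the SAP models neither cost nor use.

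2. *The schedule may be incomplete rather than the data absent.* III.d requires all measurements at 1, 2 and 2.5 years, and the SAP models MHI, which is not one of the three questionnaires and whose source is not stated. Something beyond the listed questionnaires may have been collected. This stands as a caution: what is shown is a conflict between the schedule and the stated comparison, not proof that no data were gathered.

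3. *A history is taken from every patient.* This also stands. A reader might infer that treatment history goes unrecorded, but the documents show only that prior treatments are not named as a variable. Taken alone, that is close to missing detail.

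4. *The undertaking is a background sentence.* The next sentence gives reproducibility at other institutions as the main aim, and no objective names medication use. This lowers the weight of the point. It does not remove the stated cost comparison in III.d or the long-term cost objective, both of which need the data.

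5. *Confounding by prior treatment is speculation.* Largely fair. That earlier treatment failure steers patients towards surgery is plausible, since allocation follows preference, but nothing in the documents establishes it.

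**Conclusion.** The point holds in limited form. Followed as written, the plan can show early medication change but has no scheduled data for its own comparison of medication cost at 1, 2 and 2.5 years, or for the medication and visit parts of long-term direct cost. The SAP has no medication outcome among its six.

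On size, post-treatment logging covers 2 of 30 months (6.7%) and misses at least two of the three comparison times, or all three if it starts at treatment. The 6.7% describes calendar coverage. It is not a measure of bias or lost power, and sampling a log intermittently would be acceptable if the samples fell at the analysed visits.

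This rests on reading the 2-month limit as applying to the whole list and on the list of questionnaires being complete. If either fails, the collection gap may close, but the missing SAP outcome remains. The omission of prior treatments is secondary. The questionnaire analyses are not affected, so this is a worthwhile correction and not a fatal flaw.

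**What to change.** 1. **Collection.** Repeat the medication and visit items of the diary for 30 days before each 1-, 2- and 2.5-year questionnaire, in both groups. State when the existing post-treatment log starts and which items the 2-month limit covers.
2. **SAP outcomes.** Add medication-use days per 30 days, and the Protocol's medication-cost measurement, as named secondary outcomes in the existing mixed model. Also report the baseline against the early post-treatment log, which needs no new data.
3. **Prior treatment.** Record prior preventive treatments, including prior botulinum toxin, on a structured baseline form with coding fixed in advance. Describe them by group and adjust for them in a sensitivity analysis.
4. **If follow-up is already complete**, as the SAP's past tense suggests it may be: analyse the two existing logs, take prior treatments from the recorded histories where available, and restrict the claim to early medication change.

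**Cost.** 3 × 30 = 90 extra diary days per patient at most. With 50 patients in each of two groups that is up to 100 × 90 = 9,000 patient-days, plus a short enrolment form. The burden is real but modest, since the tracking items already exist, and some missing diary data should be expected.

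### The efficacy power that set enrolment is for mean percent improvement in the Migraine Headache Index (MHI), which neither document tests, and even there 30 per group gives about 80% only for a one-sided paired test

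*Protocol*

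**What the plan says.** Protocol III.b, Sample size (power analysis), takes its efficacy inputs from an earlier single-surgeon series: "patients undergoing botulinum toxin injections had an average improvement in their Migraine Headache Index of 87.5"%, while "patients undergoing surgery had an average improvement of 96.6"%. It continues: "Assuming a standard deviation of 20%, an alpha error of 5%, and a power of 80"%, and arrives at 30 patients in each group. The cost and trigger-site calculations give 16 and 14. The largest of the three is kept and, "accounting for any participant drop-out, we will seek to enroll" 50 per group. The section does not say whether the SD is per arm or of pair differences, whether alpha is one- or two-sided, or which visit is meant.

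Protocol III.d lists headaches per 30 days, costs, MIDAS and MSQ scores. MHI and percent improvement are not on the list. The between-group instruction is "Compare all measurements between Group A and Group B using a paired t-test analysis", repeated in substance in III.g. Pairing comes from III.c: "Those patients will be matched to the individual patients in group A based on gender, age (in 5 year intervals"), migraine severity and trigger site.

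The SAP does include MHI among its six outcomes, on another scale: "Each of six outcomes were highly skewed and therefore natural logarithm was applied to each one before it was modeled", with 1 added first. The model is a linear mixed model with a random patient effect, treatment, time and their interaction. It has no matched-pair term. The SAP states "Statistical significance was defined as two-sided alpha<0.05" and gives no power for this model.

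**The concern.** Power belongs to a particular statistic, scale and test. Here the sized quantity is an arithmetic mean of per-patient percent improvements. The protocol tests the listed measurements, and the SAP tests a log-scale interaction. An effect of 9.1 points with SD 20 (9.1/20 = 0.455) fixes neither the effect nor the spread in those tests.

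Objective 1 is the surgery-versus-botulinum comparison. Anyone facing a non-significant treatment-by-time result for MHI will look to the 80% in III.b to judge whether a real difference could have been missed. That figure does not describe the test in front of them.

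**Working it through.** **Inputs from the documents.** Means 87.5% and 96.6%, so difference d = 9.1 points; SD 20; alpha 0.05; power 80%; 30 needed and 50 planned per group (III.b); two-sided 0.05 (SAP).

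**Step 1: reproduce the 30.** With z = 1.960 (two-sided) or 1.645 (one-sided), and 0.842 for power:

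- Two independent groups, SD 20 per arm: n = 2 × [20(z + 0.842)/9.1]². Result: 76 per group two-sided, 60 one-sided.
- Paired, SD of differences 20: n = [20(z + 0.842)/9.1]². Result: 37.9, so 38 pairs, two-sided; 29.9, so 30 pairs, one-sided.

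Of these four readings, only the one-sided paired one gives 30.

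**Step 2: power for percent improvement at the SAP's two-sided 0.05.** Noncentral t, with noncentrality 9.1/(20/√n) paired and 9.1/(20√(2/n)) unpaired:

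| | 30 per group | 50 per group |
|---|---|---|
| Paired, SD of differences 20 | 67% | 88% |
| Unpaired, SD per arm 20 | 41% | 62% |

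If 20 is a per-arm SD and the test is paired, the SD of differences is 20√(2(1 − ρ)) for within-pair correlation ρ. For assumed ρ of 0, 0.25, 0.5 and 0.75, power is 40, 50, 67 and 93% with 30 pairs, and 61, 73, 88 and 99% with 50. The documents give no ρ.

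**Step 3: can the effect be carried to the log scale?** Mean improvements of 87.5% and 96.6% leave mean fractions of 0.125 and 0.034. Taken as typical values, the log contrast is ln(0.125/0.034) = 1.30. But a log model compares roughly geometric means. If the fractions were lognormal with log-SDs s_B (botulinum) and s_A (surgery), the contrast would be 1.30 − (s_B² − s_A²)/2:

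- s_B = 1, s_A = 2: 1.30 + 1.5 = 2.80
- s_B = 2, s_A = 1: 1.30 − 1.5 = −0.20

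So the same arithmetic means allow a large contrast or a slightly reversed one. The added constant matters too: ln(0.125b + 1) − ln(0.034b + 1) is 0.73 at an assumed baseline MHI of b = 20 and 1.17 at b = 150.

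**Step 4: range of power on the log scale.** The documents give no log-scale SD. For a contrast of 1.30, one visit, two-sided, two independent groups (normal approximation):

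| Assumed SD of log change | n per arm for 80% | Power, 30 per arm | Power, 50 per arm |
|---|---|---|---|
| 1.0 | 10 | 99.9% | >99.9% |
| 1.5 | 21 | 92% | 99% |
| 2.0 | 38 | 71% | 90% |
| 2.5 | 58 | 52% | 74% |
| 3.0 | 84 | 39% | 58% |

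This is a one-visit simplification. It is not the SAP's four-time-point mixed model, and it ignores the Tukey adjustment.

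**The case against.** **The SAP's test is close to the sized quantity.** A treatment-by-time interaction on a log scale is about relative change from baseline, and so is percent improvement. This stands: it is the nearest planned counterpart. But step 3 shows that neither its effect nor its spread follows from the III.b inputs.

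**Enrolment is 50, not 30.** With all 50 pairs kept, the sized statistic has 88% power two-sided under the pair-difference reading. The log test may also do well. Take a simulated one-visit paired comparison with the plan's means and these assumptions: lognormal baseline with mean 100; zero shares of 57–80% (surgery) and 4–50% (botulinum); arm SDs of 14/14 or 10/17 points; no within-pair correlation. Power for change in ln(MHI+1) with 50 pairs then runs from roughly 75–84% at the low end, depending on the settings, to over 99%. A paired t-test on raw follow-up MHI is weaker, at 55–86%. This limits the consequence but does not rescue the stated figure. III.b attaches its 80% to 30 per group and presents the extra 20 as cover for drop-out (20/50 = 40%).

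**A restated power will be a wide, assumed range, and a confidence interval would tell readers more about a null result.** That is fair. It does not justify leaving an unqualified 80% in place.

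**A stronger inference that fails.** A reader might infer that an SD of 20 is impossible, since values between 0 and 100 with mean 96.6 have an SD of at most √(96.6 × 3.4) = 18.1. That bound limits the SD in a single arm. The 30 is reproduced only with 20 as the SD of pair differences, to which the bound does not apply, and III.b does not say that 20 is a per-arm figure.

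**Conclusion.** The point holds. The 80% at 30 per group is not the power of any test that the protocol or SAP plans. For percent improvement itself, it requires a one-sided paired test with 20 as the SD of pair differences. Under the SAP's two-sided 0.05, the figures are 67% paired or 41% unpaired with 30 per group, and 88% or 62% with 50. Reaching 80% would take 38 pairs or 76 per group. These results use only the plan's own inputs and a stated reading of the SD.

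For the ln(MHI+1) contrast no single figure can be given. Over assumed log-scale SDs from 3 to 1, power with 30 per arm runs from 39% to 99.9%.

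A reader might infer that the trial is underpowered for its planned analysis. The documents do not support that. They give no baseline MHI, log-scale SD, share of zeros or within-patient correlation, and plausible values put the log-scale test on either side of 80%. Nor is MHI left unanalysed, since the SAP models it. What goes untested is its mean percent improvement.

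**What to change.** - **III.b:** remove the unqualified 80% at 30 per group. Give the two-sided figures for percent improvement at 30 and 50 per group, and state whether 20 is the SD per arm or of pair differences.
- **III.b:** add power for the SAP's treatment-by-time contrast in ln(MHI+1) at one named visit, at 30 and 50 per group, as a range over assumed log-scale SD, share of zeros and within-patient correlation.
- **III.d and III.g:** add MHI to the measurements and name that contrast as the between-group efficacy test for MHI. Keep a stated between-group test for the cost and other measurements. Medication and visit costs are not among the SAP's six outcomes, so replacing every paired t-test would leave that part of objective 4 without a test.

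The cost is wording and a short calculation or simulation, with no new patients or data. The downside is that the stated power becomes an assumption-based range and may look less favourable. If the analyses have already been run, as the SAP's past tense suggests, the same text still tells readers what the 80% does and does not cover.
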